#### 9.2.3 Change in 7-point scale

Change in ordinal scale at specific time points will be summarized by proportions (e.g., proportion who have a 1-, 2-, 3-, or 4-point improvement or 1-, 2-, 3-, 4-point worsening). Mean changes from baseline to days 3, 5, 8, 11, 15 and 29 will be reported.

#### 9.2.4 Time to discharge or to a NEWS of $\leq 2$

The endpoint will be analysed with a time-to-event framework. Cox models will be used, and the survivor function will be estimated. The hazard ratio and 95% confidence interval will be provided. Participants without the endpoint being analysed will be censored on the day of the last non-missing ordinal scale assessment. The

model will adjust for age and sites. Kaplan-Meier estimates for the time to event will also be plotted.

## 9.2.5 Change in NEWS from baseline to days 8, 15 and 29

Change in NEWS at specific time points will be summarized by proportions (e.g., proportion who have a 1-, 2-, 3-, or 4-point improvement or 1-, 2-, 3-, 4-point worsening). Mean changes from baseline to days 8, 15 and 29 will be reported.

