3.7. Table of endpoints/outcomes

Objectives	Outcome Measures	Timepoint(s)
Primary Objective Participant clinical status (on a 7- point ordinal scale) In accordance with WHO recommendations the primary endpoint will be determined by a pilot trial of the first 100 participants.	 7-point ordinal scale: Not hospitalised, no limitations on activities Not hospitalised, limitation on activities; Hospitalised, not requiring supplemental oxygen; Hospitalised, requiring supplemental oxygen; Hospitalised, on non-invasive ventilation or high flow oxygen devices; Hospitalised, on invasive mechanical ventilation or ECMO (Extracorporeal membrane oxygenation) Death. 	Up to day 29
Secondary Objectives	Outcome Measures	Timepoint(s)
Evaluate the clinical efficacy of Brensocatib relative to standard care in adult patients hospitalised with COVID-19	Clinical Severity Time to an improvement of one category from admission using 7-point ordinal scale. Participant clinical status on 7-point ordinal scale Mean change in the 7-point ordinal scale	Daily whilst hospitalised Days 3, 5, 8, 11, 15 and 29. Baseline to days 3, 5, 8, 11, 15 and 29.
	National Early Warning Score (NEWS): Time to discharge or to a NEWS of ≤ 2 and maintained for 24 hours, whichever occurs first. Change from baseline Oxygenation:	Daily whilst hospitalised Days 8, 15, 29
	Oxygen free days Incidence and duration of new oxygen use during the trial	1-29 days 0-29 days
	Mechanical Ventilation: Ventilator free days	1-29 days

	Incidence and duration of new mechanical ventilation use during the trial.	1-29 days
	Hospitalisation:	
	Duration of hospitalisation (days).	Date of admission and discharge
	Mortality:	
	28-day mortality	Date of death
Evaluate the safety of the	Cumulative incidence of SAEs	1-29 days
intervention through 28 days of follow-up as compared to the control arm	Discontinuation or temporary suspension of treatment	1-29 days
	Changes in white cell count, haemoglobin, platelets, creatinine, total bilirubin, ALT, and AST over time (hospitalised participants only)	Days 0/1, 3, 5, 8, 11, 15, 29
	Adverse events of special interest- hyperkeratosis, infections and dental complications	1-29 days
	dental complications	
Exploratory Objectives	Outcome Measures	Timepoint(s)
Exploratory Objectives Evaluate the virologic efficacy of Brensocatib	·	Timepoint(s) Day 15 and day 29

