16.4. Appendix 4 – Schedule of Procedures

	Screeningd	Randomization ^d			Follow-up Assessments	Follow-up assessments	Follow-up Assessments	Unscheduled Assessments
Timeline	Day 0 or 1	Day 1 Up to 24 hours after screening	Daily whilst hospitalised	Days 3, 5 &11 ° (telephone call if at home)	Day 8° (telephone call if at home)	Day 15 ° (telephone call if at home)	Day 29 ^c (telephone call if at home ^b)	As Required in the event of AE
Informed Consent	Х				,			
Inclusion/Exclusion Criteria Check	Х	Х						
Medical History	Х							
Record Concomitant Medications	Х	Х			Х	Х	Х	Х
Check Vital Signs*^	Х	Х			X∞	X∞	X∞	X
ECG*	Х							
Full blood count*+	Х			X∞	Х∞	X∞	X∞	
Urea and electrolytes*+	Х			X∞	X∞	X∞	X∞	
Liver function tests*+	Х			X∞	X∞	X∞	X∞	
SARS CoV-2 PCR*	Χ							
Record SARS CoV-2 PCR results, only if done for clinical reasons				×	X	×	×	
Nasal swab for SARS CoV-2 PCR* (Tayside only)						X∞	Х	
Research Blood Sample * (Tayside and Sheffield only)		X			X∞	X∞	X	Х
Sputum sample for storage if available*+ (Tayside only)		X			X∞	X∞	Х	
Endotracheal aspirate sample for storage if available*+a (Tayside only)					X∞	X∞	X∞	
Clinical status on 7 point scale	Х	Х	Х	Х	Х	Х	Х	Х
NEWS recording*	Х	Х	Х	X∞	X∞	X∞	X∞	

	Screening ^d	Randomization ^d			Follow-up Assessments	Follow-up assessments	Follow-up Assessments	Unscheduled Assessments
Timeline	Day 0 or 1	Day 1 Up to 24 hours after screening	Daily whilst hospitalised	Days 3, 5 &11 ° (telephone call if at home)	Day 8° (telephone call if at home)	Day 15 ^c (telephone call if at home)	Day 29 ° (telephone call if at homeb)	As Required in the event of AE
EQ-5D questionnaire							Х	
Record supplemental oxygen*	Х	Х			X∞	X∞	X∞	Х
Record CT scan results, only if done for clinical reasons	Х	Х	Х	X∞	X∞	X∞	X∞	X∞
Pregnancy Testing (urine or blood) If Applicable	Х							
Record Adverse Events		X	Х	Х	Х	Х	Х	Х
Randomisation		X						
Dispense Trial Drugs		Χ						
Drug Return And Compliance Check							X	

[^] Vital Signs: Blood Pressure, pulse, temperature, oxygen saturation

^{*}indicates procedures that will be performed by the clinical team as part of routine care but results will be recorded and included in the eCRF. If not performed by the clinical team, but clinically indicated, the research team may assist in this being performed but all processes will avoid duplication and exposure to potentially infected participants.

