#### National Early Warning Score (NEWS):

- 1. Time to discharge or to a NEWS of  $\leq$  2 and maintained for 24 hours, whichever occurs first.
- 2. Change from baseline to days 3, 5, 8, 11, 15 and 29

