#### 7.3.1 Covariates

The primary analysis will be adjusted for the stratification variables (site and age). Baseline ordinal scale will be included if considered necessary.

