### NEWS Score, mean (SD)

Table 6: Primary outcome: Clinical status at day 29 according to treatment Group.

	Brensocatib	Placebo	Effect estimate (95%
	N =	N =	CI)
Clinical status at day 29 on the 7-point			
ordinal scale — no. of patients (%)			
Not hospitalised, no limitations on activities			
Not hospitalised, limitation on activities			
Hospitalised, not requiring supplemental oxygen			
Hospitalised, requiring supplemental oxygen			
Hospitalised, on non-invasive ventilation or high flow oxygen devices			
Hospitalised, on invasive mechanical ventilation or ECMO (Extracorporeal membrane oxygenation)			
Death			

Table 7: Secondary outcomes - Clinical Severity According to Treatment Group.

Brensocatib	Placebo	Effect estimate
N =	N =	(95% CI)

Time to clinical improvement (1 category)

Clinical status at Day 3 on the 7-point ordinal scale — no. of patients (%)

Not hospitalised, no limitations on activities

Not hospitalised, limitation on activities

Hospitalised, not requiring supplemental oxygen

Hospitalised, requiring supplemental oxygen

Hospitalised, on non-invasive ventilation or high flow oxygen devices

Hospitalised, on invasive mechanical ventilation or ECMO (Extracorporeal membrane oxygenation)

Death

Clinical status at Day 5 on the 7-point ordinal scale — no. of patients (%)

Not hospitalised, no limitations on activities

Not hospitalised, limitation on activities

Hospitalised, not requiring supplemental oxygen

Hospitalised, requiring supplemental oxygen

Hospitalised, on non-invasive ventilation or high flow oxygen devices

Hospitalised, on invasive mechanical ventilation or ECMO (Extracorporeal membrane oxygenation)

Death

Clinical status at Day 8 on the 7-point ordinal scale — no. of patients (%)

Not hospitalised, no limitations on activities

Not hospitalised, limitation on activities

Hospitalised, not requiring supplemental oxygen

Hospitalised, requiring supplemental oxygen

Hospitalised, on non-invasive ventilation or high flow oxygen devices

Hospitalised, on invasive mechanical ventilation or ECMO (Extracorporeal membrane oxygenation)

Death

Clinical status at Day 11 on the 7-point ordinal scale — no. of patients (%)

Not hospitalised, no limitations on activities

Not hospitalised, limitation on activities

Hospitalised, not requiring supplemental oxygen

Hospitalised, requiring supplemental oxygen

Hospitalised, on non-invasive ventilation or high flow oxygen devices

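### The Cox model for time to discharge or NEWS of 2 or less omits baseline NEWS, a scheduled and probably prognostic covariate: the analysis is valid but may give up precision

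*SAP*

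**What the plan says.** The Protocol (3.7, Table of endpoints/outcomes) defines the endpoint as "Time to discharge or to a NEWS of ≤ 2 and maintained for 24 hours, whichever occurs first". SAP 4.2 repeats it.

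SAP 9.2.4 analyses it with a Cox model, reports a hazard ratio with a 95% confidence interval, and sets the covariates: "model will adjust for age and sites. Kaplan-Meier estimates for the time to event will also be plotted".

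The only baseline severity covariate named in the SAP is in 7.3.1: "Baseline ordinal scale will be included if considered necessary". That sentence follows one about the primary analysis, is optional, and refers to the ordinal scale rather than to NEWS. No other section adds baseline NEWS to the 9.2.4 model.

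The value is available. The row "NEWS recording" in Protocol Appendix 4 (repeated in SAP 5.4) is marked at both screening and randomisation. SAP Table 5 will summarise NEWS at randomisation by arm, and SAP 9.2.5 needs it for change from baseline.

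**The concern.** One of the two routes to the event is a fixed NEWS threshold. For that route, a participant entering at NEWS 3 must fall 1 point and one entering at NEWS 9 must fall 7. Discharge is likely to depend on entry severity as well, though less directly. Severity at entry can vary widely, because any one of five criteria is enough for inclusion (SAP 5.2.1), from a low lymphocyte count to a need for supplemental oxygen. Randomisation is stratified by site and age only, so neither the design nor the model takes account of baseline NEWS.

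In a Cox model with a real treatment effect, leaving out a prognostic covariate has two consequences. The test loses power, and the estimated hazard ratio moves towards 1 compared with the hazard ratio for patients of the same baseline NEWS. What is at stake is the precision and the interpretation of one secondary endpoint.

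**Working it through.** **1. The plan's own figures.** No power, event count or target hazard ratio is stated for this endpoint. The stated sample sizes concern the primary ordinal outcome. They reproduce with the Whitehead formula, N = 12(z₁₋α/₂ + z₁₋β)² / [(ln OR)²(1 − Σp̄³)]. For OR 1.75 and 85% power, the averaged arm proportions give Σp̄³ = 0.160, so N = 12 × (1.960 + 1.036)² / (0.3132 × 0.840) = 409.5, against 412 in SAP Table 3. They say nothing about time to discharge or NEWS of 2 or less, so the size has to be shown as a range.

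**2. Inputs.**
- From the documents: 400 participants, 1:1 allocation, two-sided 5%, follow-up to day 29.
- Assumed: hazard ratio conditional on NEWS of 1.35; 85% of placebo participants with the event by day 29 (75% as an alternative); baseline NEWS SD of 2.2 (1.5 and 3.0 as alternatives); and a range of prognostic strengths.

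Both models include age. Site was left out of both for simplicity.

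**3. Anchor with no prognostic effect.** The Schoenfeld approximation is power = Φ(√(d/4) × ln HR − 1.960). The simulated trials averaged 354 events: √88.5 × 0.3001 − 1.960 = 0.863, giving 80.6%. Simulation gave 79.1% without and 79.2% with baseline NEWS. Event times in whole days pull the mean estimate to 1.338 even here, so attenuation due to omission is the gap between the two models, not the distance from 1.35.

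**4. Range of prognostic strength** (1,500 to 2,000 runs per row; Monte Carlo error about 1 point per power figure):

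| Event HR per NEWS point | Log HR per SD | HR without → with NEWS | Power without → with | Loss (points) |
|---|---|---|---|---|
| 1.00 | 0 | 1.338 → 1.338 | 79.1% → 79.2% | 0.1 |
| 0.95 | 0.05 × 2.2 = 0.11 | 1.334 → 1.337 | 78.3% → 79.1% | 0.8 |
| 0.90 | 0.10 × 2.2 = 0.22 | 1.326 → 1.337 | 76.3% → 78.5% | 2.2 |
| 0.82 | 0.20 × 2.2 = 0.44 | 1.295 → 1.334 | 68.5% → 77.2% | 8.7 |
| 0.74 | 0.30 × 2.2 = 0.66 | 1.259 → 1.328 | 57.0% → 75.4% | 18.4 |

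Attenuation in the last three rows: 1.337 − 1.326 = 0.011; 1.334 − 1.295 = 0.039; 1.328 − 1.259 = 0.069.

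**5. A second parameterisation** (placebo daily hazard 0.10, strength set directly per SD, 300 to 400 runs, Monte Carlo error about 2.5 points per figure). Power without → with baseline NEWS:
- 0: 79.7% → 80.0%
- 0.1: 78.2% → 77.5%
- 0.2: 80.0% → 81.5%
- 0.3: 73.3% → 78.3%
- 0.5: 67.7% → 77.7%
- 0.7: 55.3% → 74.3%

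The losses at 0.3, 0.5 and 0.7 are 5, 10 and 19 points. At 0.1 and 0.2 the difference is within noise. On the per-SD scale the two sets agree.

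**6. Sensitivity to the other assumptions.**
- 75% placebo events: loss 0.8 to 16.5 points over 0.95 to 0.74 per NEWS point.
- True HR 1.25: 0.5 to 13.8 points over 0.90 to 0.74 per point. True HR 1.5: 1.1 to 12.6 points.
- NEWS SD 1.5 or 3.0, at 0.82 per point: 4.1 (73.0% → 77.1%) or 15.1 (60.9% → 76.0%) points.

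**7. Validity of the planned model.** With a true hazard ratio of 1.0, at every prognostic strength and both event rates, the mean estimate was 1.001 to 1.003 and rejection was 3.2% to 4.6%, with or without NEWS.

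**The case against.** The planned model is a legitimate analysis. It adjusts for both stratification factors, and because the Cox hazard ratio is non-collapsible, the hazard ratio given age and site is a proper quantity in its own right. Power is not the declared currency here: no power is stated for this endpoint, SAP 9.2.4 promises an interval without a p-value, Protocol 10.2 says secondary hypotheses will be described by summary statistics, and SAP 7.6 does not list this endpoint among the key secondaries of the preliminary analysis. Every numerical input beyond the design constants is assumed. The simulations also treat NEWS as independent of age, leave out site, and replace a composite of discharge and NEWS with a single hazard and no deaths. If severity tracks age or site, the planned covariates absorb part of it and the loss is smaller.

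All of this stands, and it makes the change an efficiency gain, not the correction of an error. Power should be read as a stand-in for the width of the interval. It does not remove the point: nothing in the documents suggests that age and site carry the information in baseline NEWS, and adding the term cost nothing visible when NEWS had no effect.

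A reader might also infer that baseline NEWS exists for everyone and fixes the distance to the event for everyone. The documents do not support that. NEWS is scheduled for everyone but taken from routine care, so some values may be missing, and a participant can reach the event by discharge. Nor does a chance imbalance in NEWS go unseen: the confidence interval allows for it and SAP Table 5 displays it.

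**Conclusion.** SAP 9.2.4 leaves out a covariate that is scheduled, already tabulated, and likely to be prognostic for this endpoint. With 400 participants, a conditional hazard ratio of 1.35 and 29 days assumed, the expected cost in power by log HR per SD of baseline NEWS is:
- weak (up to about 0.2): about 0 to 2 points;
- moderate (about 0.25 to 0.5): about 3 to 10 points;
- strong (about 0.65 to 0.7): up to about 18 to 19 points.

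The attenuation due to omission is about 0.01 to 0.07 on the hazard ratio scale, and close to nil at the weakest strengths. The documents cannot say which band applies.

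A reader might infer that the planned hazard ratio is wrong, that the test is invalid, or that the trial is underpowered. None of these follows. The estimate is nearer 1 only relative to the hazard ratio conditional on baseline NEWS, and only if there is an effect. Under the null there is no bias and no excess of false positives. The sample size rests on the primary outcome and is unaffected.

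**What to change.** Reword the covariate sentence of SAP 9.2.4 along these lines: the Cox model will adjust for age, site and baseline NEWS, entered as a continuous variable, using the randomisation value recorded before the first dose, or the screening value if that is missing. Report this hazard ratio and 95% confidence interval as the result for the endpoint, and keep the age-and-site model as a sensitivity analysis. The pre-dose condition needs stating because Protocol 7.8 takes the NEWS nearest 8am, while Protocol 8.7 allows the first dose at different times of day.

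In the same edit, say how participants already at NEWS 2 or less at baseline are handled in the analysis. Infiltrates or a low lymphocyte count alone can qualify a patient, so such participants are possible, and neither document says whether they count as early events, contribute only through discharge, or are set aside.

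The cost is a sentence or two and one degree of freedom, with no new data. The change should be dated before results by arm for this endpoint are seen. The preliminary analysis in SAP 7.6 does not list it, so that is still possible on the face of the plan. If the results have been seen, the NEWS-adjusted model should be labelled post hoc.

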It is expected that these clinical assessments will be carried out by the clinical team during routine clinical care and documented on a NEWS chart. Where the assessments have been carried out, the results of the assessment closest to 8am on the day will be used to prevent duplication and further exposure of the trial staff to patients with COVID-19.

- Blood pressure and pulse, lying or seated
- Tympanic temperature
- SpO2
- Record if SpO2 has been measured on air or oxygen concentration the participant was receiving.

Ordinal Scale

The ordinal scale is an assessment of the clinical status on a given trial day. Each day, the worst score for that day will be recorded. The scale is as follows:

- 1. Not hospitalised, no limitations on activities
- 2. Not hospitalised, limitation on activities;
- 3. Hospitalised, not requiring supplemental oxygen;
- 4. Hospitalised, requiring supplemental oxygen;
- 5. Hospitalised, on non-invasive ventilation or high flow oxygen devices;
- 6. Hospitalised, on invasive mechanical ventilation or ECMO;
- 7. Death.

NEWS Score

The NEWS score has demonstrated an ability to discriminate patients at risk of poor outcomes. (Smith, 2016). This score is based on 7 clinical parameters. The NEWS2 Score is being used as an efficacy measure.

This should be evaluated at the assessment recorded closest to 8am on a given trial day. These parameters can be obtained from the hospital chart.

Exploratory assessment- viral shedding

Where practical at the Tayside site only, nasal swabs will be obtained on day 15 and day 29 to evaluate viral clearance by PCR.

Exploratory assessment- neutrophil studies

At the Tayside and Sheffield sites only, additional blood will be taken for isolation of peripheral blood neutrophils, as per outcome measures section 3.7.

Exploratory assessment- quality of life

The validated EQ-5D-5L quality of life tool will be administered to patients who are able to complete the questionnaire either in person (those still in hospital) or over the telephone (those at home) to determine the impact of treatment on quality of life.

Clinical Evaluation

As these participants are in-patients receiving care for COVID-19, they will be monitored as per clinical need. Where already obtained for clinical need the following blood results will be recorded at days 1, 3, 5, 8, 11, 15, 29:

- White cell count, haemoglobin, platelets, neutrophils, eosinophils, lymphocytes
- creatinine, eGFR
- AST and ALT

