10.5. Interim analysis and criteria for the premature termination of the trial

For reasonable cause, the PI may terminate a participant's participation in the trial prematurely. The Sponsor may decide to terminate the trial prematurely. If this occurs, written notification of the trial

termination is required to be sent to all the sites. Some conditions that may warrant trial termination include the following:

- · Discovery of an unexpected, significant, or unacceptable risk to the participants in the trial,
- Decision on the part of the funder to suspend or discontinue development of the investigational product,
- Decision by a regulatory authority or the Sponsor to stop the trial at any time, were applicable.

If the trial is prematurely terminated, all participants who received a dose of any of the trial drugs and have not completed their trial period will be discontinued from the trial drug immediately; all the safety procedures required to be performed will be conducted. All discontinued participants will be followed up by a phone call 30 days after discontinuation for collection of AEs. The Sponsor will notify the appropriate Regulatory bodies in the respective countries regarding the reason for terminating the trial.

The DMC will evaluate the results of the trial in an unblinded fashion for safety. Participant population

The participant populations whose data will be participated to the trial analysis – both for the primary analysis and any applicable secondary analyses will be all-treated population, i.e. any participant randomised into the trial that received at least one dose of trial drug. Procedure(s) to account for missing or spurious data will be detailed in the SAP.

The primary analysis will be based on the intention-to-treat principle. The extent of missing data will be examined and the reason for drop-out ascertained. Multiple imputation may be used to impute missing values if necessary and where assumptions for missing at random data are met. Where imputation is used, a sensitivity analysis will be conducted considering only cases without missing data. Complete case analysis where missing participants are excluded will be carried out as a secondary analysis.

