⁺Excess biological samples that are being taken for clinical reasons may be stored for future use if no longer required for clinical purposes (Tayside only).

^a For those participants who are intubated.

[∞]These assessments will not be completed if the participant has been discharged from hospital.

^b For the Tayside and Sheffield site only, the day 29 assessments will be carried out face-to-face either at a NHS facility or at the participant's home. Home visits will only be carried out if no one in the household has symptoms of COVID-19.

^cResearch blood samples (Tayside and Sheffield only) and, once discharged, assessments may be completed within +/- 1 day

^dScreening and randomisation may occur on the same day if all eligibility criteria are met. Day of first dose of IMP will be considered as day 1 for the calculation of follow up assessments.

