## 7.4 Missing Data

(ICH E3; 9.7.1, 11.4.2.2. ICH E9;5.3. EMA Guideline on Missing Data in Confirmatory Clinical Trials)

All reasonable efforts will be taken to minimise loss to follow-up, which is expected to be minimal as data collection for primary and secondary outcomes using trial-specific eCRFs is combined with linkage to routine clinical data on study outcomes. The number and percentage of participants with follow-up information at day 29 after the randomisation will be reported. For all participants who were discharged and alive but have missing clinical status, a clinical status scale of 2 (Not hospitalised, limitation on activities) will be applied.

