Hospitalised, on invasive mechanical ventilation or ECMO (Extracorporeal membrane oxygenation)

Death

Clinical status at Day 15 on the 7-point ordinal scale — no. of patients (%)

Not hospitalised, no limitations on activities

Not hospitalised, limitation on activities

Hospitalised, not requiring supplemental oxygen

Hospitalised, requiring supplemental oxygen

Hospitalised, on non-invasive ventilation or high flow oxygen devices

Hospitalised, on invasive mechanical ventilation or ECMO (Extracorporeal membrane oxygenation)

Death

Clinical status at Day 29 on the 7-point ordinal scale — no. of patients (%)

Not hospitalised, no limitations on activities

Not hospitalised, limitation on activities

Hospitalised, not requiring supplemental oxygen

Hospitalised, requiring supplemental oxygen

Hospitalised, on non-invasive ventilation or high flow oxygen devices

Hospitalised, on invasive mechanical ventilation or ECMO (Extracorporeal membrane oxygenation)

Death

Change in 7-point ordinal scale

Day 3

Day 5

Day 8

Day 11

Day 15

Day 29

Table 8: Secondary outcome: National Early Warning Score (NEWS)

	Brensocatib N =	Placebo N =	Effect estimate (95% CI)
Time to discharge or to a NEWS of <= 2			
Change in NEWS from baseline			
Day 8			
Day 15			
Day 29			

Table 9: Secondary outcome: Oxygenation, mechanical ventilation, hospitalisation, and mortality

Brensocatib	Placebo	Effect estimate (95% CI)
N =	N =	

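### Change in NEWS at days 8, 15 and 29 exists only for participants still in hospital, so its effect estimate compares groups selected by the outcome

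*SAP*

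**What the plan says.** - **Outcome.** Protocol 3.7 lists change from baseline in NEWS at days 8, 15 and 29 as a secondary efficacy outcome. SAP 9.2.5 plans the proportions improving or worsening by 1 to 4 points, and: "Mean changes from baseline to days 8, 15 and 29 will be reported".
- **Reporting.** Shell Table 8 has a block titled "Change in NEWS from baseline" for days 8, 15 and 29, under a column for an effect estimate with 95% CI. SAP 9.2.5 names no method for that estimate.
- **Collection.** In protocol Appendix 4 and SAP Table 1, the row "NEWS recording" carries the ∞ mark at every follow-up visit. The footnote reads: "These assessments will not be completed if the participant has been discharged from hospital". Day 29 keeps the mark although Tayside and Sheffield see participants face-to-face that day. Protocol 7.8 takes the score from inpatient records: "These parameters can be obtained from the hospital chart". The 7-point scale has no such mark and is collected by telephone after discharge.
- **Missing values.** The one fill-in rule in SAP 7.4 is for the ordinal scale: "For all participants who were discharged and alive but have missing clinical status, a clinical status scale of 2" is applied. Protocol 10.5 adds a general option: "Multiple imputation may be used to impute missing values if necessary and where assumptions for missing at random data are met". SAP section 8 bases percentages on non-missing data.
- **Companion endpoint.** The other NEWS outcome, "Time to discharge or to a NEWS of ≤ 2 and maintained for 24 hours, whichever occurs first", counts discharge as success.

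**The concern.** Protocol section 1 expects the drug to shorten hospital stay. If it does, it changes who has a NEWS at each visit: participants who recover leave the denominator, as do those who die. The means and improvement proportions then set patients who have not recovered on one arm against patients who have not recovered on the other. That is a comparison within a group defined after randomisation, and it does not estimate the effect on NEWS in the randomised population. More values are missing in the arm that does better, and those left on each arm tend to look alike. A reader of Table 8 could take a near-zero estimate with a confidence interval as evidence that the drug does not affect physiological severity.

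**Working it through.** **Inputs from the documents.** Control distribution in protocol Table 4, from death to home without limitation: 2, 1, 2, 7, 8, 38, 42%. Odds ratio 2 in Table 6; odds ratio 1.75 as the revised target in protocol 10.1. N = 400 allocated 1:1, taken as 200 per arm with no loss.

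**Step 1: reproduce the plan's figures.** Whitehead's formula is N = 12(z₀.₉₇₅ + z₀.₈₅)² / [ln(OR)² (1 − Σp̄³)], where p̄ is the mean of the two arms' proportions in each category. It gives 269.7 at odds ratio 2 (stated 272) and 409.5 at 1.75 (stated 412). Halving the cumulative odds gives a treated column of 1.01, 0.51, 1.04, 3.82, 4.73, 29.73, 59.15%, which matches Table 6 to rounding. Unrounded values are used below unless Table 6 is named.

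**Step 2: who can have a NEWS.** Alive in hospital means ordinal categories 3 to 6.
- Control: 8 + 7 + 2 + 1 = 18%, or 36 of 200.
- Treated, odds ratio 2: 4.7 + 3.8 + 1 + 0.5 = 10%, or 20 of 200.
- Treated, odds ratio 1.75: 11.3%, or about 23 of 200.
- Without a NEWS at odds ratio 2: (164 + 180)/400 = 86%.

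**Step 3: severity mix among inpatients**, categories 3/4/5/6.
- Control, dividing by 18: 44/39/11/6%.
- Treated (Table 6), dividing by 10: 47/38/10/5%.

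**Step 4: benefit before and after restriction, on the ordinal scale.** This needs no assumption about NEWS. The control mean in all participants is 7(0.02) + 6(0.01) + 5(0.02) + 4(0.07) + 3(0.08) + 2(0.38) + 1(0.42) = 2.00. The control mean in inpatients is (24 + 28 + 10 + 6)/18 = 3.78.

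| | All: control v treated | Difference | Inpatients: control v treated | Difference | Share lost |
|---|---|---|---|---|---|
| OR 2 | 2.00 v 1.63 | 0.37 | 3.78 v 3.74 | 0.04 | 89% |
| OR 1.75 | 2.00 v 1.70 | 0.30 | 3.78 v 3.74 | 0.04 | 88% |

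At odds ratio 2 the standard error of the inpatient difference is 0.235 with 36 and 20 patients. The chance of p < 0.05 is about 5%, no better than with no effect.

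**Step 5: NEWS points, on assumed inputs.** The documents give no NEWS mean or SD, so this step is illustrative. Assumptions: latent severity follows proportional odds; baseline NEWS mean 5, SD 2; follow-up NEWS SD 3; correlation of severity with baseline NEWS 0 to 0.6 and with follow-up NEWS 0.5 to 0.8; 2% of controls dead; 200 per arm; 1,000 runs per setting; t-test. The full difference is hypothetical, because it gives a score to discharged and dead participants too.
- Visit with 20% of controls in hospital or dead, as in Table 4: a full difference of −0.46 to −0.92 points becomes −0.00 to −0.44 in inpatients. Power falls from 27–92% to 2–10%.
- Earlier visits, with 35%, 50% or 70% of controls assumed in hospital or dead (odds ratio 1.75; correlations 0.3 and 0.8): about −0.75 becomes −0.25, −0.33 and −0.40. Power falls from 63–66% to 7%, 12% and 20%.

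**The case against.** - **SAP 9.2.5 reads as descriptive.** It names no test or model, whereas sections such as 9.2.6 to 9.2.11 mostly state a comparison between arms. The effect-estimate column in Table 8 may be a generic header: it also stands over daily clinical status in Table 7 and laboratory changes in Table 10, where the text plans description only. This largely stands, and it is why the main fix is to align the shell with the text. It does not remove the point: as written, the shell calls for an estimate and CI with no stated method, in a subset that is not labelled as such.
- **Numbers may already be shown.** SAP section 8 lists the non-missing n for continuous variables. Table 8, however, has one N per arm and no count by visit.
- **Multiple imputation.** The protocol 10.5 option is discretionary and depends on missing at random. Absence caused by recovery or death does not fit that condition, the dead have no NEWS to impute, and the SAP does not carry the option over to NEWS.
- **The benefit is captured elsewhere.** This stands. The primary ordinal analysis includes discharge and death, time to discharge or NEWS ≤2 counts discharge, and NEWS change is not a key secondary endpoint in the preliminary analysis (SAP 7.6).

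**Conclusion.** The point holds as a defect in a secondary endpoint. The planned NEWS-change summaries, and the estimate in Table 8, describe only participants alive in hospital. Under the plan's own distribution about 85% of participants would have no value, and 88–89% of the ordinal benefit would vanish from the inpatient comparison. That size rests on the Table 4 proportions, proportional odds and 200 per arm. It applies to one visit, which the documents date inconsistently: the Table 6 caption says day 15 and the text of protocol 10.1 says day 29.

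Three stronger readings are tempting and not supported.
- A reader might infer that a real benefit disappears at all three visits. With many still in hospital, as may be so at day 8, up to about half of the difference remained in the settings tried, though power was still low.
- A reader might infer that the comparison tends to reverse. The average differences were zero or in favour of treatment; the wrong sign in 26–49% of simulated trials at the 20% visit is what sampling noise around a small difference produces.
- A reader might infer that the trial's main conclusion is at risk. It is not, since the primary analysis counts every category.

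All magnitudes in NEWS points depend on assumed values.

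**What to change.** In SAP 9.2.5 and shell Table 8:
1. Label mean change and improvement proportions as descriptive among participants in hospital at the visit.
2. Show the number contributing per arm at each visit, beside the numbers discharged alive and dead.
3. Remove the effect estimate and CI from these rows.
4. If a between-arm NEWS comparison is wanted, add a supportive analysis of all participants in the analysis set: discharged alive ranked best, inpatients ranked by NEWS change from baseline, death ranked worst, with the age and site adjustment used elsewhere. State how an inpatient with no charted NEWS is ranked.

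While editing, reconcile the visit days: SAP 4.2 lists NEWS change at days 3, 5, 8, 11, 15 and 29, but SAP 9.2.5 and the protocol list only days 8, 15 and 29.

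**Cost.** Items 1 to 3 are wording. Item 4 needs one derived variable from data already collected. In the same simulation, an unadjusted Wilcoxon test on that ranking had 52–56% power at odds ratio 1.75 and 68–72% at odds ratio 2 at the 20% visit, against 3–7% and 2–10% for the inpatient mean change. The downsides are real: it gives a rank comparison, not a difference in NEWS points; about 80% of controls and 89% of treated participants would tie at the best rank under Table 6; and it overlaps with the ordinal scale. It should therefore stay supportive, with change from baseline kept as the protocol defines it.
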